Aim 3. Examine the feasibility and acceptability of the internet-delivered mindfulness-based intervention (iMBI), called “Mindfulness-based Queer Resilience (MBQR)”, for HIV prevention. We will enroll and randomize a sample of 60 distressed, high-risk YMSM into one of two groups: MBQR intervention ($n=30$) or active control condition ($n=30$). We will aim to over enroll YMSM of color (e.g., Black/Latinx YMSM) and anticipate the group to include **approximately 50-60% Black/Latinx YMSM (or YMSM of color)**. Primary outcomes are **HIV and STI testing** and self-reported sexual risk behaviors. Secondary outcomes are stress biomarker (fingernail cortisol levels), psychological health, minority stress and coping. The study will examine recruitment and retention, number of sessions attended, self-reported at-home practice of mindfulness, completion of assessment, and acceptability of the intervention.

2. Aim 3 Study Design Overview

[figure not shown]
The methodological approach includes a 2-arm trial of MBQR vs. a *health education* control group, with up to $n=30$ per arm (total Aim 3 sample size = up to 60 participants enrolled and randomized). The study is intended to evaluate the impacts of MBQR on the outcomes outlined in the Specific Aims above.

All research assessments will take place digitally using Qualtrics, LLC (Provo, UT, USA) survey management tool. Participants will be sent secure links via email and SMS that can be accessed with their participant identification number. The MBQR intervention classes will be offered online via Zoom by a trained and qualified mindfulness instructor.

Baseline assessment links will be sent to all enrolled participants and completed prior to the start of the interventions. Follow up assessments will be conducted at three time points (post-intervention, 6-months follow up, and at 1-year follow up (for intervention participants only)).

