Participants who were randomized to the control group will be offered a MBQR-hybrid course after the 6-month follow-up assessment is complete. This additional course is optional. Control group members who opt to take MBQR-hybrid will be invited to complete a post-intervention assessment and exit interview. The total length of involvement for control group participants who opt not to take MBQR-hybrid will be around 6-months from the time of enrollment to the time of the final research assessment, while control group participants opting into the MBQR-hybrid will be done with participation in the study around 9-12 months after enrollment. Participants randomized to the MBQR intervention group will be invited to complete a 1-year follow up assessment in addition to the other assessments, thus their involvement in the study will last around 12 months from the time of enrollment. The study interventions last 10 weeks and take place in the first two months of study involvement.

The figure below provides a visual outline of the study flow, including the screening and assessment sequence.

3. Selection Criteria for Aim 3:

The following is the most updated inclusion/exclusion criteria:

- Inclusion criteria:
 - (1) assigned male at birth,
 - (2) being 18 to 34 of age,
 - (3) identify as a cisgender man or nonbinary,
 - (4) reside in the United States,
 - (5) can read and speak English,
 - (6) engaged in condomless anal sex with another man in past 6 months,
 - (7) endorse distress, measured by the PHQ-9 and GAD-7,
 - (8) possess a device (phone, tablet, computer) that allows for online conferencing.
 - (9) HIV-negative at time of screening
- About HIV status: HIV status will be assessed in 2 steps: (1) by self-report in online survey and (2) by rapid HIV testing via Zoom with a trained study RA (optional; other options could include local testing or by self-report). We will provide rapid oral HIV testing in Aim 3. At screening, participants will participate in rapid oral HIV testing (optional), and at post-intervention and follow-up, participants will engage in both HIV and STI testing (see more in HIV/STI testing protocol).
- Exclusion criteria: YMSM will be excluded from the study if they are determined to have symptoms that would prevent them from giving meaningful consent or participate in study activities including any of the following criteria:
 - (1) Significant cognitive impairment
 - (2) Psychosis
 - (3) Imminent suicidal risk

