- c. A covariate adaptive randomization process will be used, balancing groups based on race (white vs. non-white); anxiety/depressive symptomology (high vs. moderate); and gender identity (cis-male vs. non-binary) if sample size allows for this.

4) Care Packages:

- a. Prior to the start of the interventions, all participants (intervention and control) will be sent a study care package, which will contain a yoga mat, condoms, lubricant, raisins, pen, journal, stickers, and a fidget spinner / stress ball, along with a brief description and purpose for each of the items.

Weekly Assessments, Post-Intervention and Follow-up Procedures

1) *Weekly Assessments:* During the 10-week intervention period, participants will be sent invites (via Qualtrics- individualized links) to complete weekly assessments designed to capture: (a) monitoring of sexual risk (condomless sex); (b) monitoring of depression (PHQ-9) and anxiety symptoms (GAD-7); and (c) self-report of weekly/daily practice time spent on intervention. Participants will be compensated \$5 per each weekly assessment completed (up to \$50 total).

2) *Post-Intervention Assessment:*

- a. Similar to the baseline survey, participants will be asked to complete a post-intervention assessment via Qualtrics. The assessment is estimated

to take 60 minutes to complete, and participants will be compensated \$30 for their time.

- b. Cortisol genetic testing kits and STI/HIV self-tests will be mailed out to participants post-intervention. Participants will be compensated \$20 for each completed test (\$40 total).

3) *Exit Interviews (Intervention Group Only):*

- a. Semi-structured interviews with intervention group participants will be conducted one-on-one via Zoom post-intervention to gather qualitative feedback on the study intervention.
- b. Interviews are estimated to take 90-120 minutes.
- c. Participants will be compensated \$40 for their time.

4) *6-month Follow Up Assessment:*

- a. Similar to the baseline and post-intervention surveys, participants will be asked to complete a 6-month follow up assessment via Qualtrics. The assessment is estimated to take 60 minutes to complete, and participants will be compensated \$30 for their time.
- b. Cortisol genetic testing kits and STI/HIV self-tests will be mailed out to participants post-intervention. Participants will be compensated \$20 for each completed test (\$40 total).

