- c. This will be the final assessment for control group participants. Following their study involvement, control group participants will be given the option to participate in a MBQR-hybrid program. This additional course is optional. Control group members who opt to take MBQR-hybrid will be invited to complete a post-intervention assessment and exit interview.

5) *1-year Follow Up Assessment (Intervention Group Only):*

- a. Intervention participants will be asked to complete a final 1-year follow up assessment via Qualtrics. The assessment is estimated to take 60 minutes to complete, and participants will be compensated \$30 for their time.
- b. Cortisol genetic testing kits and STI/HIV self-tests will be mailed out to participants post-intervention. Participants will be compensated \$20 for each completed test (\$40 total).
- c. This will be the final assessment for intervention group participants.

5. MBQR Intervention and Health Education Control:

Mindfulness-Based Queer Resilience (MBQR):

MBQR is an online, Zoom-based mindfulness course that meets 2.5 hour per week for ten weeks, facilitated by queer mindfulness teachers, with weekly home practice and additional reflection and reading activities that can be completed by participants independently via study website portal.

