MBQR is designed to alleviate the burden of minority stress and mental health and promote HIV testing and healthy sex behaviors among young adult gay men, bisexual men, queer men, and non-binary people assigned male at birth. Principles of MBQR include (a) reducing minority stress as a key theoretical guide, (b) affirming LGBTQ + identity and facilitating healthy identity development, (c) attending to intersectionality, (d) facilitating resilience and self-empowerment, (e) trauma sensitivity, and (f) promoting healthy relationships and a healthy community. Key techniques include through attention regulation to facilitate agency and self-awareness, enhancing emotion regulation, reducing reactivity to minority stress-informed thoughts, self-compassion to increase self-acceptance, and reducing behavioral avoidance. Formal and informal mindfulness practices will be offered, such as mindful walking, body scan, attention practice, self-compassion, etc. In addition to the 10 weekly sessions there is an all-day retreat (6hrs) that takes place around week 5. The participants also meet one-on-one with the instructor at the beginning and middle of class for a 30-minute welcome call and check in.

Health Education Active Control:

The online Health Education course, used as an active control in the RCT, is a self-paced program that can be largely completed independently (no group meeting, no all-day) by control group participants. The ten weekly modules are estimated to take 30 to 90 minutes each to complete and consist of readings, videos, infographics, and other related activities (e.g., reflections, quizzes).

The purpose of the health education course is to provide participants with general information on health, factors that affect health, and to promote health behaviors. Topics include sleep, exercise, healthy eating and body image, time management, alcohol and substance use, sexual health, school/work life balance, and healthy relationships. This information is provided without an emphasis on mindfulness.

Mindfulness-Based Queer Resilience (MBQR)-hybrid:

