MBQR-hybrid is an online-based mindfulness course asynchronously facilitated by queer mindfulness teachers, with weekly home practice and additional reflection and reading activities that can be completed by participants independently via study website portal. Participants will also have the option of participating in weekly live 1-hour sessions. MBQR-hybrid is designed to be completed within a 3-months time frame (10 modules that can be paced to complete in a 10-14 weeks time frame).

6. Other Study Details:

Compensation

Participants will have the opportunity to earn up to \$340 (intervention group) and up to \$300 (control group) for their time and effort in this study. Participants will only be compensated for the study components that they choose to complete. Partial

compensation will not be provided. If a participant withdraws from the study early, they will not be compensated for the study components that are incomplete.

Below is an outline of the compensation structure by study element.

T1: Baseline (\$40 Total)

\$20 - HIV testing**

\$20 - Cortisol nail sample

Intervention / Control (\$50 Total)

\$50 - \$5 per assessment x 10

T2: Post-Intervention (\$70 - 110 Total)

\$20 - STI/HIV testing

\$20 - Cortisol nail sample

\$30 - Assessment

\$40 - Exit Interview*

T3: 6-Month Follow Up (\$70 Total)

\$20 - STI/HIV testing

\$20 - Cortisol nail sample

\$30 - Assessment

T4: 1-year* Follow Up (\$70 Total)

\$20 - STI/HIV testing

\$20 - Cortisol nail sample

\$30 - Assessment

*MBQR Intervention Group Only; Control group will be invited to take part in a MBQR-hybrid course after their 6-month follow up is complete. This additional course is optional. Control group members who opt to take MBQR-hybrid will be invited to complete a post-intervention assessment and exit interview (\$30 and \$40 each).

**Compensation for HIV testing is not limited to the self-testing kit provided by the study.

Total Possible Compensation for Control Participants = \$300

Total Possible Compensation for Intervention Participants = \$340

Withdrawal during intervention

We anticipate some amount of dropout during the study. If a participant in MBQR decides to withdraw from the study during the course or if a control participant discontinues the health education training, they will still be invited to take part in the follow up assessments.

Confidentiality

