Mindfulness-based Queer Resilience (MBQR) to Promote Mental and Sexual Health among Sexual and Gender Minority Young Adults: Statistical Analysis Plan

A mixed-methods approach will be used to understand feasibility and acceptability of this randomized controlled trial. Descriptive statistics will be used to summarize feasibility and acceptability measures from the full sample. These measures include recruitment rates, retention/attrition rates, session attendance, Client Satisfaction Questionnaire, and session evaluation form.

In addition, qualitative data from exit interviews will be analyzed using template analysis, a thematic analysis methodology that applies data reduction techniques for rapid turnaround, often used in intervention development and refinement research.

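### The SAP summarises retention/attrition over the full sample and plans no by-arm summary, so the planned figure would not identify MBQR retention or show differential attrition

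*SAP*

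**What the plan says.** The SAP consists of two short paragraphs. The first contains its one rule for quantitative data: "Descriptive statistics will be used to summarize feasibility and acceptability measures from the full sample". The sentence after it lists the measures: recruitment, retention/attrition, attendance, a satisfaction questionnaire and session evaluations. The second paragraph covers the qualitative analysis of exit interviews. Arm is mentioned in neither.

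The protocol (section 1, Aim 3) states the aim as "Examine the feasibility and acceptability of the internet-delivered mindfulness-based intervention (iMBI", which is MBQR. Sixty participants are to be randomised, 30 per arm.

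The programmes are described in section 5. MBQR meets live for 2.5 hours a week over ten weeks and adds a 6-hour retreat and one-on-one calls with the instructor. The control course "is a self-paced program that can be largely completed independently (no group meeting, no all-day) by control group participants", in ten modules of 30 to 90 minutes each.

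Both arms are assessed at post-intervention and at 6 months. A further assessment takes place "at 1-year follow up (for intervention participants only" (section 2). Later, "Participants who were randomized to the control group will be offered a MBQR-hybrid course after the 6-month follow-up assessment is complete", and "Control group members who opt to take MBQR-hybrid will be invited to complete a post-intervention assessment and exit interview" (sections 2 and 4). Section 6 anticipates some dropout without giving a rate, and says that people who stop either programme are still invited to follow-up.

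**The concern.** Aim 3 asks about one programme, while the planned summary covers participants in two. Scheduled group time in MBQR is 10 × 2.5 + 6 = 31 hours, before one-on-one calls and home practice. The control modules take an estimated 10 × 0.5 = 5 to 10 × 1.5 = 15 hours, with no fixed meetings. Unequal retention is therefore plausible, in either direction.

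Two things are at stake. A pooled figure could look reassuring while MBQR itself retained people poorly, or look mediocre while MBQR retained them well. It would also conceal differential attrition, which whoever designs a larger trial with these two arms would want to see.

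**Working it through.** **Inputs.** From the protocol, sections 1 and 2: 30 MBQR + 30 control = 60, which agrees with the stated total. No retention rate, target or precision calculation appears in either document, so there is no planned figure to reproduce. All retention rates below are assumptions.

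**1. How far the pooled rate can be from the MBQR rate.** At 1:1 allocation, pooled = (MBQR + control)/2, so pooled − MBQR = (control − MBQR)/2. The pooled figure misses the MBQR rate by half the between-arm gap, and by nothing if there is no gap.

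**2. What a pooled count implies for MBQR.** If T of 60 are retained, the MBQR count lies between max(0, T − 30) and min(30, T).

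| Pooled (assumed) | MBQR retention that fits | Largest hidden gap |
|---|---|---|
| 42/60 (70%) | 12/30 to 30/30 (40–100%) | 60 points |
| 45/60 (75%) | 15/30 to 30/30 (50–100%) | 50 points |
| 48/60 (80%) | 18/30 to 30/30 (60–100%) | 40 points |
| 51/60 (85%) | 21/30 to 30/30 (70–100%) | 30 points |
| 54/60 (90%) | 24/30 to 30/30 (80–100%) | 20 points |

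The ends of each range are arithmetic limits, not forecasts.

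**3. What a by-arm table would add.** Three splits that all pool to 48/60, with exact (Clopper-Pearson) 95% intervals per arm and the Newcombe 95% interval for MBQR minus control:

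| MBQR | Control | Difference |
|---|---|---|
| 24/30, 80% (61–92) | 24/30, 80% (61–92) | 0 points (−20.2 to +20.2) |
| 21/30, 70% (51–85) | 27/30, 90% (73–98) | −20 points (−39.0 to +0.5) |
| 18/30, 60% (41–77) | 30/30, 100% (88–100) | −40 points (−57.7 to −20.9) |

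All three would appear in the planned summary as 80%, with exact interval 68–89%.

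**4. Which listed measures are affected.**
- Retention/attrition at post-intervention and 6 months: affected, because both arms are assessed then.
- Recruitment: not affected. It precedes randomisation, so the full sample is the right basis.
- One-year completion: due only for MBQR, so the only need is to state that denominator.
- Live-session attendance: within the randomised comparison this is MBQR-only, since the control course has no meetings.
- Client Satisfaction Questionnaire: affected only if controls complete it. The protocol leaves survey content to a separate assessment document.

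**The case against.** The strongest reply is that full sample names the analysis set, everyone in the trial, and is not an instruction to merge the arms. The SAP's opening sentence also takes the randomised trial itself as the object of the feasibility work, and for that object overall recruitment and retention are coherent summaries. Both points stand, so it would be wrong to infer that the SAP prohibits by-arm tables or that an overall retention figure is a mistake. What remains is that, on either reading, no by-arm summary is planned, and the feasibility of a two-arm trial includes retention in each arm.

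A second reply is that MBQR-specific evidence exists: class attendance, practice logs and diaries, exit interviews confined to the intervention group in the randomised phase, and the 1-year visit. This is true, and acceptability of MBQR does not rest on one pooled number. But none of these gives MBQR retention at post-intervention or 6 months. Attendance cannot stand in for it, because someone who leaves the course is still invited to assessments.

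A third reply is that arm is recorded, so the table can be produced at reporting anyway. That is why the remedy is cheap, but it does not put the table in the plan.

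A reader might also infer that satisfaction scores will be pooled across arms, or that assessments from controls who take MBQR-hybrid will be mixed with the randomised-period ones, since both are called post-intervention and hybrid participants may join live sessions ("Participants will also have the option of participating in weekly live 1-hour sessions"). The documents support neither inference. They do not say who completes the satisfaction questionnaire. The compensation outline labels T2 and T3 separately, and the hybrid assessment comes after the controls' final scheduled one. One clarifying sentence is enough for the hybrid data.

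**Conclusion.** The point holds for retention/attrition at post-intervention and 6 months. As written, the plan yields a figure that need not equal MBQR retention and cannot show a difference between arms. The actual size is unknown. Under 30 per arm and an assumed pooled 80%, MBQR retention could be anywhere from 60% to 100%; at an assumed 90%, from 80% to 100%. If the arms retain equally, nothing is lost.

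For the satisfaction questionnaire the point is conditional on controls completing it. It is a gap in planned reporting and should be closed. It does not call for a different sample size. Nor should a reader expect the by-arm table to establish that attrition is balanced: with 24/30 in both arms, the difference interval still runs to about 20 points either way.

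**What to change.** Keep the full-sample summaries of recruitment and overall retention, and add to the SAP:

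> Retention/attrition at post-intervention and 6 months is also summarised by randomised arm (denominator: everyone randomised to that arm), as counts and percentages with 95% CIs. One-year completion and live-session attendance are reported over everyone randomised to MBQR. Client Satisfaction Questionnaire and session evaluation forms are summarised by arm for whichever arms complete them, with the number responding. Data collected during or after MBQR-hybrid are summarised separately; those controls' earlier data through 6 months stay in the control arm.

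The last clause matters. Setting aside all data from controls who later choose the hybrid course would remove participants from the control arm because of a choice made after 6 months, and would contradict the stated denominator.

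The cost is a short paragraph. No new data, visits or participants are needed, because each participant's arm is known. The drawback is precision: at 80% retention the exact 95% interval is 61–92% for 30 participants against 68–89% for 60, so the by-arm figures are descriptive.

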Meditation-related risks: The National Center for Complementary and Integrative Health (NCCIH) states that meditation is generally safe for healthy people, but that adverse effects have also been reported.³⁴ Undesirable side effects and risks of meditation have been documented in more than 40 scientific reports [for reviews see³⁵⁻³⁷] and are listed in the Mindfulness-Based Intervention Guidelines.^{38,39} More common, less serious side effects that have been reported by individuals within the context of MBIs or of individuals who are meditating less than an hour per day include: increased depression, anxiety or panic, re-experiencing of traumatic memories, dissociation, executive dysfunction, headaches/body pain and insomnia.^{35,40-45} A few case reports of more serious side effects including mania, psychosis, and suicidality have been reported, mostly in the contexts of intensive retreats (>5 hrs/day) or in conjunction with pre-existing psychopathology.^{35,37,38,46} The frequency of serious adverse effects in the context of MBIs is estimated to be less than 1%, although adequate estimates are not available.⁴⁷

A number of actions have been taken to minimize meditation-related risks at different stages of the study. During the pre-enrollment stage, individuals with severe mental illness that could preclude regular class attendance or impact group participation (i.e., symptomatic, untreated bipolar disorder or a history of psychosis and/or schizophrenia) are excluded from the study and all risks are clearly communicated in the consent form. During treatment, meditations are relatively short and interspersed with dyads and reflections. Mindfulness homework assigned as part of the intervention is optional and is recommended to not exceed 1 hour per day. Teachers query participants about their experiences with meditation, and provide corrective feedback or modifications when needed. Developing strategies for working with physical and emotional discomfort is an explicit goal of the program. Because not all participants feel comfortable disclosing difficulties in class, an online “safety check-in” questionnaire will query meditation-related risks.

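### The SAP plans no by-arm summary of weekly PHQ-9/GAD-7 worsening or of adverse events, so in the planned analysis worsening followed by dropout shows only as attrition

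*SAP*

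**What the plan says.** The SAP is two paragraphs long. Its quantitative sentence reads "Descriptive statistics will be used to summarize feasibility and acceptability measures from the full sample", followed by the list: "These measures include recruitment rates, retention/attrition rates, session attendance, Client Satisfaction Questionnaire, and session evaluation form". The second paragraph covers template analysis of exit interviews. PHQ-9, GAD-7, adverse events and comparisons by arm are not mentioned.

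The protocol bears on this in four places:

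- Section 4, Weekly Assessments: during the 10-week period participants receive weekly online surveys that include "monitoring of depression (PHQ-9) and anxiety symptoms (GAD-7").
- Section 6, Compensation: the $50 for ten weekly assessments sits under "Intervention / Control", so both arms complete them.
- Section 6, Meditation-related risks: the more common, less serious side effects listed are "increased depression, anxiety or panic, re-experiencing of traumatic memories, dissociation, executive dysfunction, headaches/body pain and insomnia".
- Section 3, Selection Criteria: participants must "endorse distress, measured by the PHQ-9 and GAD-7", so the trial enrols on these same two scales.

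**The concern.** The protocol names increased depression and anxiety as side effects of this type of course, and it measures depression and anxiety symptoms weekly in both arms. The analysis plan then makes no use of the measurements. Acceptability is a stated aim, and a trial analysed as written could call MBQR acceptable on attendance and satisfaction without tabulating how many participants got worse.

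The control arm matters here. Some participants will fluctuate upward whatever they are assigned to, and only the same weekly series in the health education arm shows how often that happens without MBQR.

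Dropout matters too. If someone's scores rise and they then stop responding, the weekly scores already on file may be the only record of what happened. The planned tables would show that person as one unit of attrition and nothing more.

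**Working it through.** **1. Are the weekly scores collected in both arms?** The compensation schedule in Protocol section 6 settles this, because its stated totals can be rebuilt.

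- Control: 40 (T1) + 50 (weekly, 10 × 5) + 70 (T2) + 70 (T3) + 30 + 40 (hybrid assessment and interview) = $300, as stated. Without the weekly line it is $250.
- Intervention: 40 + 50 + 110 + 70 + 70 = $340, as stated.

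The control total is reached only if control participants complete the weekly assessments. At up to 30 per arm there are up to 10 × 30 = 300 scores per arm on each scale.

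**2. Does any planned analysis use them?** The SAP's word for its list leaves it open, but only to further feasibility and acceptability measures. Neither document plans a PHQ-9/GAD-7 summary, a worsening count, an adverse event table or a by-arm display.

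**3. Does another source cover the same ground in both arms during the course?** The safety check-in questionnaire (Meditation-related risks) has no stated timing, arm or analysis. Exit interviews at post-intervention are for the MBQR arm only. Adverse events depend on being observed or reported, and no score change is defined as one. The weekly scores are the only harm-relevant measure that the documents show repeated in both arms during the course.

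**4. What could the data show?** Exact (Clopper-Pearson) 95% intervals for x worsening out of n use the Beta quantiles: lower = Beta(0.025; x, n−x+1), upper = Beta(0.975; x+1, n−x).

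| Worsened | 95% interval |
|---|---|
| 0/30 | 0 to 11.6% |
| 3/30 | 2.1 to 26.5% |
| 6/30 | 7.7 to 38.6% |

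Thirty is the maximum. For zero events the upper limit is 1 − 0.025^(1/n): 11.6% at n = 30, and 16.8% if only 20 contributed (an assumed figure).

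Under assumed rates and two-sided alpha 0.05, 30 per arm gives 19%, 49% and 78% power for worsening of 10% against 20%, 30% and 40%. The data support estimates with intervals, not a test.

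**5. Which count should be used?** Ten weeks on two scales gives a full completer 20 scores. Someone leaving after week 3 has 6. Let p be the assumed probability that a score crosses the margin by noise alone, with independent errors. The chance of at least one crossing is 1 − (1−p)^k.

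| p | k = 20 (completer) | k = 6 (leaves after week 3) |
|---|---|---|
| 1% | 18% | 6% |
| 2.5% | 40% | 14% |
| 5% | 64% | 26% |

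Positive correlation between weeks would lower these figures. An any-week count therefore undercounts early leavers, and it biases the arm difference if survey completion differs. The last available score gives every contributing participant one chance per scale.

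Requiring two consecutive weeks also helps. At p = 2.5% each pair of weeks crosses with probability 0.025² = 0.000625. A completer has 9 pairs × 2 scales = 18, so the chance is at most 18 × 0.000625 = 1.1%. The early leaver has 2 × 2 = 4 pairs, so at most 0.25%. Correlated errors would raise these figures, so the number of completed surveys still has to be shown beside the count.

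**6. Why count individuals?** With assumed values, if 20% worsen by 5 points and 80% improve by 4, the mean change is 0.2 × 5 − 0.8 × 4 = −2.2, an apparent benefit. With 10% or 30% worsening it is −3.1 or −1.3. A mean alone can hide a minority who worsen.

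**The case against.** The strongest reply is that the protocol already handles harms. Section 6, Safety Monitoring, has adverse events documented by staff and continuously reviewed by the principal investigator, and serious ones go to the IRB. Adverse events that lead to dropout are a monitored category of their own. The safety check-in asks about meditation-related problems. People who leave the course are still invited to the follow-up assessments.

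This stands, and it limits the point. A reader might infer that worsening would go wholly unreported, or that someone who worsens and leaves is recorded by the trial as attrition and nothing else. The documents support neither reading: such a person may be picked up as an adverse event or seen at follow-up. Nor do they rank depression or anxiety as the leading harm of these courses. They appear in a list with several others.

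The reply does not reach the analysis. Monitoring by the investigator and IRB does not say what will be tabulated. A score rise on an online form has no stated route to becoming an adverse event, and an invitation to follow-up is not data.

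Three further objections have some force:

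- The SAP also gives no analysis for the primary outcomes or for cortisol, so this is part of a wider gap. The point here is confined to harms, where an ordinary outcome analysis of mean scores would not be enough.
- The eligibility text gives no PHQ-9/GAD-7 cut-off, so the size of any average fall from regression to the mean cannot be derived. The mean-change figures are illustrative only, and no mean-change analysis is planned.
- The content of the baseline survey is in a separate document, so it cannot be confirmed that PHQ-9 and GAD-7 are repeated there. The fix allows for this.

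**Conclusion.** The point holds for the planned analysis, not for the conduct of the trial. PHQ-9 and GAD-7 are collected weekly in both arms, match harms that the protocol names, and enter no planned summary. Adverse events enter none either. Worsening followed by dropout would appear in the SAP's outputs only within the retention/attrition rate.

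The consequence is a one-sided basis for judging acceptability, and it can be avoided with data already collected. What can be gained is bounded by the sample: with a full 30 in an arm, seeing no worsening would still leave rates up to 11.6% compatible with the data. The by-arm difference can be described but not tested with useful power unless the true gap is very large. The power and chance-crossing figures rest on assumed rates, and the latter on independent errors.

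**What to change.** Add to the SAP a descriptive harms table by arm as randomised:

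1. **Main measure.** For PHQ-9 and GAD-7 separately, the number and percentage whose last available score in the intervention period exceeds the pre-randomisation score by a reliable-worsening margin fixed before data are viewed. The reference is the baseline survey if it contains the scale, otherwise screening. Give exact 95% intervals and the between-arm difference with its interval. Include participants who stop the course or the surveys, using their scores up to that point, and show how many have no weekly score.
2. **Supportive measure.** Worsening sustained on two consecutive weekly assessments, shown with the number of weekly assessments completed per arm.
3. **Attrition and events.** Among participants counted as attrition, how many had met the margin beforehand, with adverse events and reasons for dropout by arm.

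The cost is one paragraph and one table. The intervals will be wide, so results should be labelled descriptive. The margin is an analysis definition only and sets no rule for clinical management.
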